5.7 Handling of dropouts, missing data and outliers

Outliers will be included in summary tables and listings and will not be handled separately in any analyses. Generally, no imputation of data will be performed. However, clinical safety laboratory parameters that are outside the detection limit, will be replaced with the detection limit when calculating statistics. Also, when calculating statistics for PK plasma concentrations, concentrations under LLOQ will be replaced with LLOQ if more than 50% of the values for a given time point is above LLOQ. Otherwise, no statistics will be calculated for that time point. For imputation of PK plasma concentration under LLOQ with the purpose of calculating PK parameters, see section 6 below.

λ_{z} , the first order rate constant associated with the terminal portion of the curve will be determined by lin-logarithmic regression of the terminal elimination phase of individual plasma concentration vs time curves. Determination of λ_{z} requires identification of a sufficiently linear terminal phase (as determined by visual inspection of the lin-log plasma concentration vs time plot with the regression line) consisting of at least 3 terminal concentration values (not including C_{max}). If this is not achieved, λ_{z} and its dependent PK parameters will not be reported for that profile. In the following cases, λ_{z} dependent PK parameters will be flagged in listings as potentially unreliable:

- λ_{z} estimation is based on a period of less than 1.0 times the resulting $T_{1/2}$.
- The adjusted R² value of the regression line is < 0.85.
- The estimated % extrapolated AUC is > 20% $((AUC_{\text{inf}} - AUC_t) / AUC_{\text{inf}}) * 100$.

Where plasma nicotine concentrations are above LLOQ immediately prior to product administration (pre-dose sample), PK parameters will also be calculated from baseline adjusted concentrations using a subject's elimination rate constant (λ_{z}) (from the curve during the specific treatment period) and observed pre-dose concentration (considered to have been collected at time 0). Baseline adjustments will be calculated according to the formula:

$$C(t)_{\text{adjusted}} = C(t)_{\text{observed}} - C(0)e^{-\lambda_{\text{z}}t}$$

In cases of a generated negative $C(t)_{\text{adjusted}}$, the value will be replaced with zero.

Where plasma nicotine concentrations are below LLOQ immediately prior to product administration (pre-dose sample), baseline adjusted PK parameters will be considered the same as non-baseline adjusted PK parameters.

For subjects where λ_{z} cannot be calculated, baseline adjusted PK parameters (C_{max} , AUC_t , T_{max} , C_{last} , AUC_{0-90} , AUC_{inf} and $T_{1/2}$) will not be generated and reported. For subjects where λ_{z} can be calculated but where the acceptance criteria for λ_{z} determination have not been fulfilled, baseline adjusted PK parameters will be calculated, but reported PK parameters will then be flagged in listings as potentially unreliable.

In addition to PK parameters specified in the protocol, t_{last} (the time of C_{last}), $AUC_{\text{extr} \%}$, λ_{z} and details about λ_{z} determination (adjusted R², span, number of timepoints and lower/ upper timepoints used for λ_{z} calculation) will be presented in the listing section.

If there is a confirmed dosing error during the study, the PK data for that period will only be included in the listings but excluded from descriptive and statistical analyses. In case of missed blood samples, potential impact on PK parameters will be assessed for each individual case. PK parameters with a high degree of uncertainty due to missing samples (e.g. multiple

CONFIDENTIAL

Document name: IB-OND-ZONEX-11_SAP_v1.0_23NOV2021

samples missing around C_{\max}) will be flagged as unreliable in the report and may in rare cases be excluded from summary tables, descriptive statistics, and statistical analysis.

7 CLINICAL DATABASE PROCESSING

7.1 General information

The standards set forth by the Clinical Data Interchange Standards Consortium (CDISC) will be followed. CDISC develops and publishes standards in order to normalise the structure of clinical study data and thereby simplify submissions to and reviews by authorities such as the Food and Drug Administration (FDA). These standards include naming conventions, code lists, and data structure formats.

The study data will be structured into a database model reflecting the Study Data Tabulation Model (SDTM) and be compliant to SDTM Implementation Guide (SDTM-IG) version 3.2. The data used for statistical analysis will be structured to reflect the Analysis Data Model (ADaM) and be compliant to ADaM Implementation Guide (ADaM-IG) version 1.1. Both SDTM and ADaM are data-model standards developed by CDISC, and the versions used are mentioned as preferred versions in the FDA data standards catalogue.

Data values are collected according to, or mapped into, Controlled Terminology (CT) codelists defined by CDISC, whenever possible. The codelists are updated annually at CTC and the latest version available at study start will be used. As per default, CT codelists will be used in all tables, listings, and figures. Custom codelists for test or parameter names will be used if applicable upon Sponsor's request, to align with protocol texts, or to adhere to other standard naming conventions (e.g. PK parameter name "Tmax" will be used instead of the CDISC term "Time of CMAX"). These custom codelists will be mapped in the "Parameter Name" field in the ADaM structure, while the CT will be kept in the SDTM predecessor fields to provide traceability back to CDISC codelists.

7.2 Database modeling of study design

The SDTM study design model contains the following structural components:

[figure not shown]
EPOCH: Study epochs follow a controlled terminology to represent the different study parts (e.g. SCREENING, TREATMENT [X], FOLLOW-UP)

ELEMENT: Building blocks used to build up the entire study length for all subjects. Information on ELEMENTs are extracted from the study design and schedule of events in the protocol. ELEMENTs are defined to span the entire study without gaps. One EPOCH may contain one or several ELEMENTs. All ELEMENTs must have transition rules in accordance with the protocol to determine start and end.

ARM: Subjects are allocated to study arms depending on the study design, either by randomisation or other allocation processes defined in the study protocol. ARMs are defined as the total number of planned ways a subject can go through the study (unique combination of study ELEMENTs). All ARMs must contain a unique sequence of ELEMENTs.

VISIT: Study visits are defined as planned timepoints during the study where study data is collected. A visit can be performed in clinic, by off-site contact with study personnel (phone call, video conference or similar), or by subject initiated recordings of data. The visit schedule is extracted from protocol and eCRF design.

Below is a schematic representation of the SDTM study design:

8 STATISTICAL METHODOLOGY

All relevant collected data will be listed. Additional statistical analyses and descriptive summaries are specified below.

8.1 Primary endpoint(s) analysis

8.1.1 C_{max} and AUC_t

This section refers to the primary objective 1, endpoint 1.1.

C_{max} and AUC_t and baseline adjusted C_{max} and AUC_t will be summarised descriptively. Also, log transformed nicotine C_{max} and AUC_t estimates will be evaluated separately in a linear mixed-effects analysis of variance model with fixed effects for product and a random effect for subject. The above product differences will be back-transformed to present the ratios of geometric least squares (LS) means coupled with the 90% confidence intervals (CIs). If the CI falls within the range of 0.8-1.25, the corresponding two products are considered equivalent with respect to that comparison.

8.1.2 Tables and Figures relating to the primary endpoint(s)

Analysis and output related to the primary endpoint(s) are specified under section statistical output layout. The following tables and figures relate to the primary endpoint(s):

Table 14.4.1 PK parameters (Pharmacokinetic analysis set)

Table 14.4.2 PK parameters – Normalised by dose (Pharmacokinetic analysis set)

Error! Reference source not found.

8.2 Secondary endpoint(s) analysis

8.2.1 Definition of endpoint(s)

8.2.1.1 Other Pharmacokinetic parameters T_{max} , C_{last} , AUC_{0-90} , AUC_{inf} and $T_{1/2}$ and and baseline adjusted T_{max} , C_{last} , AUC_{0-90} , AUC_{inf} and $T_{1/2}$

This section refers to the secondary objective 2.1, endpoints 2.1.1.

See Section 6. All PK parameters (and PK parameters normalised by dose) will be summarised descriptively.

8.2.1.2 Extracted dose of nicotine

This section refers to the secondary objective 2.2, endpoint 2.2.1.

Content pre-use is calculated by multiplying the mean content of the weight normalised reference samples with the pouch weight of the study pouches. Content post-use is the measured content left in the study pouches post-use. Extracted amount (mg/unit) of nicotine, for each pouch, is calculated as the difference of content pre-use and content post-use, i.e.:

Equation 1

$$\frac{(D \times E_i) - F_i}{i = 1, \dots, N}$$

where N =number of study pouches used in analysis

D = Mean content of weight normalised reference samples

E_i = Weight of the unused pouch

F_i = Content post-use

D is calculated by:

$$D = \frac{\sum_{j=1}^M C_j}{M},$$

where $C_j = \frac{A_j}{B_j}$ is weight normalised content for reference samples, and A_j =reference nicotine amount and B_j =reference weight, $j = 1, \dots, M$. M =Number of reference samples .

Extracted fraction (%) of nicotine, for each pouch $i = 1, \dots, N$, is calculated as the extracted amount divided by the content pre-use, i.e.:

Equation 2

$$\frac{(D \times E_i) - F_i}{D \times E_i}$$

Extracted dose of nicotine will be summarised descriptively and analysed using a Wilcoxon signed rank test to assess differences between IPs.

Pearson correlation coefficients for baseline adjusted AUC_{inf} , AUC_t , baseline adjusted AUC_{inf} and baseline adjusted AUC_t and the derived extracted dose of nicotine (attained via Equation 1 above) will be estimated and presented for each IP, with corresponding p-value.

CONFIDENTIAL

Document name: IB-OND-ZONEX-11_SAP_v1.0_23NOV2021

8.2.1.3 *Product evaluation scale (PES)*

This section refers to the secondary objective 2.3, endpoint 2.3.1.

Each question of the PES will be answered using a 7-point Likert scale. Responses will be presented as the following factor scores: 1 = not at all, 2 = very little, 3 = a little, 4 = moderately, 5 = a lot, 6 = quite a lot, 7 = extremely.

Four multi-item subscales will be derived from the PES categories:

- "Satisfaction" (items 1, 2, 3, and 12)
- "Psychological Reward" (items 4-8)
- "Aversion" (items 9, 10, 16, and 18)
- "Relief" (items 11, 13, 14, 15, and reversed for item 20)

These four multi-item subscales will be summarized descriptively by IP and overall, at applicable assessment timepoints. Single items 17, 19 and 21 will also be summarized in the same way as the multi-item subscales. Also, PES sub-category and total scores will be presented visually with individual and mean figures.

In addition, PES-differences between products on total and sub-category PES score, at each time point, will be analysed using Wilcoxon Rank Sum tests.

8.2.1.4 *Product preference scale (PPS)*

This section refers to the secondary objective 2.3, endpoint 2.3.1.

PPS will be summarised descriptively by IP. The PPS data collected in the eCRF will therefore be derived so the results will be presented by IP, instead of presented by day (as collected) i.e., derived according to the following:

Rank the 4 pouch products in relation to each other.				Rate the 4 pouch products in order of preference			
Study product used at:	Order of preference:			Study product:	Preference result:		
Day 1	(1)	2	3	4	Product A	1	2
Day 2	1	2	3	(4)	Product B	(1)	2
Day 3	1	2	(3)	4	Product C	1	(2)
Day 4	1	(2)	3	4	Product D	1	2

➡

Note: this is just an illustrative example with made up subject evaluations, to explain the data derivation. The table layout for PPS can be found in Table 14.2.3 Products preference scale (PPS) (Full analysis set)

8.2.1.5 *Urge to use questionnaire*

This section refers to the secondary objective 2.3, endpoint 2.3.1.

The answer from the Urge to use questionnaire is graded on a Visual Analogue Scale (VAS) from 0-100 mm, where 0 is "No urge at all" and 100 is "extreme urge".

The following parameters will be calculated for the urge to use assessments:

- E_{max} - The maximum change from baseline VAS score ($VAS_{pre-use} - VAS_{post-use}$).
- $T_{E_{max}}$ - Time of the E_{max} . If the maximum value occurs at more than one time point, $T_{E_{max}}$ will be defined as the first time point with this value.

CONFIDENTIAL

Document name: IB-OND-ZONEX-11_SAP_v1.0_23NOV2021

- AUEC₀₋₁₂₀ - The area under the change from baseline VAS score versus time curve from time 0 to 120 minutes, calculated using the linear trapezoidal method with linear interpolation using actual sample times.

Responses and the derived parameters mentioned above will be summarized by IP and overall using descriptive statistics, including change from baseline. Also, urge to use questionnaire (VAS score) will be presented visually with individual and mean figures.

8.2.1.6 Adverse events

This section refers to the secondary objective 2.4, endpoint 2.4.1.

An overview of all AEs, including SAEs, intensity, relationship to IP, and deaths will be presented by IP and overall. Incidence of AEs and SAEs will also be summarised by SOC and PT by IP and overall. For both summaries, any AE that occurred during follow-up, will be presented separately (in an own column, in the same tables).

8.2.1.7 Safety laboratory analyses

This section refers to the secondary objective 2.4, endpoint 2.4.2.

Clinical laboratory data will be summarised by IP with absolute and percent change from baseline.

8.2.1.8 Vital signs

This section refers to the secondary objective 2.4, endpoint 2.4.2.

Vital signs (systolic/diastolic blood pressure and pulse) will be summarised by IP. Data will be presented with absolute and percent change from baseline.

8.2.1.9 12-lead ECG

This section refers to the secondary objective 2.4, endpoint 2.4.2.

All ECGs will be categorised as "normal", "abnormal, not clinically significant", or "abnormal, clinically significant" (as judged by the Investigator) and summarised by IP using frequency tables.

Figure 14.2.2 Products evaluation scale (PES) sub-category and total scores mean graphs (Full analysis set)

Figure 14.2.3 Urge to use (VAS score) individual graphs (Full analysis set)

Figure 14.2.4 Urge to use (VAS Score) mean graphs (Full analysis set)

Figure 14.4.1 Individual plasma concentrations over time (lin-log) (Pharmacokinetic analysis set)

CONFIDENTIAL

Document name: IB-OND-ZONEX-11_SAP_v1.0_23NOV2021

Figure 14.4.2 Individual plasma concentrations over time (lin-lin) (Pharmacokinetic analysis set)

Figure 14.4.3 Mean plasma concentrations over time (lin-log) (Pharmacokinetic analysis set)

Figure 14.4.4 Mean plasma concentrations over time (lin-lin) (Pharmacokinetic analysis set)

8.3 Tertiary/exploratory endpoint(s) analysis

NA

8.4 Other data analysis/presentation

8.4.1 Demographics and baseline characteristics

Descriptive statistics for demographics, physical examinations, weight and height will be presented by sequence.

8.4.2 Medical/surgical history and prior/concomitant medication

Medical/surgical history will be presented by system-organ-class (SOC) and preferred term (PT). Prior/concomitant medications will be presented by ATC level 3 and 5.

Medical/surgical history and prior medications will be presented overall by descriptive statistics and listings. Concomitant medications will be presented by sequence.

In addition to the primary and secondary endpoint(s) described above, the following tables and figures will be produced:

Table 14.1.1 Baseline characteristics and demographics (Full analysis set)

Table 14.1.2 Subject disposition (all subjects)

Table 14.1.3 Medical history events by system organ class and preferred term (Full analysis set)

Table 14.1.4 Concomitant medications by ATC levels 3 and 5 (Full analysis set)

Table 14.1.5 Prior medications by ATC levels 3 and 5 (Full analysis set)

8.5 Interim analysis

NA

9 CHANGES FROM THE CSP

9.1 Changes of product comparisons for primary analysis

In the protocol (Synopsis and Section 17.5) it was stated that the primary objective will be examined by the following statistical comparisons for AUC and C_{max} :

- Product A versus Product B, C and D, respectively

CONFIDENTIAL

Document name: IB-OND-ZONEX-11_SAP_v1.0_23NOV2021

- Product B versus Product C and D, respectively
- Product C versus Product D

Instead, the primary objective will be examined by the following statistical comparisons for AUC_t and C_{max} :

- Product A does not significantly differ from Product D
- Product B does not significantly differ from Product D
- Product C does not significantly differ from Product D

The reason for the change is that the test products are Products A-C and the Comparator product is Product D, so there is no need for multiple comparisons.

9.2 Changes of fixed effects for primary analysis

In the protocol (Synopsis and Section 17.5) it was stated that the linear mixed-effects model for the primary analysis should include fixed effects for period, sequence, and product, and a random effect for subject. The fixed effects for period and sequence will be removed for the statistical analysis. The subjects will be allowed to use their own nicotine containing products ad lib after the 8-hour timepoint until 10 pm. Hence, keeping period and sequence in the model adds no extra value to the analysis.

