#### Visit 2 (In-clinic treatment period, Day -1 to Day 4)

At Visit 2, subjects will be admitted to the clinic on Day -1 and will remain at the clinic until Day 4 for daily single IP use and PK blood sampling, nicotine extraction, subjective questionnaire assessments and safety assessments.

On Day -1, baseline vital signs, ECG and clinical laboratory profile assessments will be performed. Subjects are allowed to use their own snus or nicotine pouch product until 10 pm of Day -1. On Day -1 the subjects will also undertake a familiarisation session of the study products and questionnaires. The clinical team will explain how the products will be used and the subjects will have the opportunity to see the product and packaging. An explanation of how the questionnaires will be distributed to the subjects will be given. The familiarisation session does not include a product trial and the products used in the session will not be used in the clinical study but will be retained as demonstration samples for accountability purposes.

In the morning of Day 1, after pre-use assessments and confirmation of eligibility, the subjects will be randomised and then administered a single pouch of the IP in the sequence to which they have been randomised. Oral nicotine IP will be used for 20 minutes according to standard use instructions. PK sampling will be done pre-IP use and at 5, 10, 15, 20, 25, 30, 45, 60, 90 minutes, 2, 4, 6 and 8 hours post start of IP use. Used pouches will be collected for analysis of nicotine extraction. Questionnaires will be distributed to the subject at defined intervals throughout the day. Safety will be followed throughout the day. Subjects will be allowed to use their own nicotine containing products *ad lib* after the 8-hour timepoint until 10 pm.

In the morning of Day 2, after pre-IP use assessments, the subjects will be administered a single pouch of the IP in the sequence to which they have been randomised. IP will be used for 20 minutes according to standard use instructions. PK sampling will be done pre-IP use and at 5, 10, 15, 20, 25, 30, 45, 60, 90 minutes, 2, 4, 6 and 8 hours post start of IP use. Used pouches will be collected for analysis of nicotine extraction. Questionnaires will be distributed to the subject at defined intervals throughout the day. Safety will be followed

throughout the day. Subjects will be allowed to use their own nicotine containing products *ad lib* after the 8-hour timepoint until 10 pm.

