### 9.6.1 **General restrictions**

- Subjects shall abstain from snus and all other nicotine containing products from 10 pm the evening prior to the anticipated start of each IP use on Days 1 to 4.
- Use of other nicotine-containing products, than defined by this study protocol, is not allowed during the study from 10 pm Day-1 until the end of Visit 2.
- Subjects are not allowed to eat or drink or conduct any other mouth related procedure (e.g. tooth brushing) 30 minutes before IP use, during IP use and 30 minutes after the IP has been taken out.
- Meals and Dietary Restrictions:

Meals will be served while the study subjects are in the research clinic. Breakfast will be served approximately 1 hour prior to IP use. Lunch will be served 4 hours after start of each IP use. Snack, dinner and evening snack will be served approximately 7, 9 and 11 hours post-IP use, respectively. Water is allowed *ad lib* at the clinic except 30 minutes before IP use until 30 minutes after IP use on Days 1 to 4.

- Alcohol: Consumption of alcohol is not allowed within 48 hours prior to the screening visit or Visit 2. Consumption of alcohol is not allowed during the subject's stay at the clinic during Visit 2.
- Drugs of abuse: Use of drugs of abuse is not allowed during the study. In addition to the urine drug testing described in Table 8.1-1, additional random testing can be performed at the clinic visits.
- Coffee: Not more than 5 cups of coffee per day will be allowed from admission to the clinic on Day -1 until the end of Visit 2.
- Xanthine or taurine containing products/beverages: Energy drinks (e.g. Red bull) are not allowed from admission to the clinic on Day -1 until the end of Visit 2.
- Exercise: The subjects must refrain from strenuous exercise (defined as greater than 70% of the maximal pulse rate for one hour or more) during Visit 2.

- Blood donation: The subjects must not donate blood or plasma during the study until 3 months after the end of Visit 2.
- Participation in other clinical studies: Study subjects are not allowed to participate in any other interventional clinical study during the study period.
- Visits to the clinic: Subjects are not allowed to leave the research clinic during study visits, unless authorised by the study personnel.

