#### 9.8.3 *Subject replacement*

Subjects who are prematurely withdrawn from the study for any reason may be replaced during the course of the study.

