Log transformed nicotine  $C_{max}$  and  $AUC_t$  estimates will be evaluated separately in a linear mixed-effects analysis of variance model with fixed effects for period, sequence, and product, and a random effect for subject. If the assumptions for this model will be inappropriate will the fixed effects period and sequence be removed from the model. The above product differences will be back-transformed to present the ratios of geometric least squares (LS) means and 95% CIs of each test product versus each other from the same model.

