4.5 Randomisation

On Day 1, subjects will be randomised to one of 4 treatment sequences. The 4 different products are:

- A: ZoneX [REDACTED] nicotine/pouch
- B: ZoneX [REDACTED] nicotine/pouch
- C: ZoneX [REDACTED] nicotine/pouch
- D: [REDACTED] nicotine/ pouch (comparator product)

The 4 randomisation sequences are described in the table below:

Sequence	Order			
Sequence 1	A	B	C	D
Sequence 2	B	C	D	A
Sequence 3	C	D	A	B
Sequence 4	D	A	B	C

A computer-generated randomisation list will be created by CTC using SAS Proc Plan, SAS Version 9.4 (or later). The randomisation list will contain subject number, sequence and treatment and will be kept by the randomiser until database lock. A copy of the randomization list will be provided to the research clinic.

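### SAP 9.2 drops period from the primary cross-over model outright, for a reason that does not support dropping it

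*SAP*

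**What the plan says.** Protocol 17.5.1 (and the synopsis) fits log Cmax and log AUCt separately with fixed period, sequence and product and a random subject effect. It then gives a condition for simplifying the model: "If the assumptions for this model will be inappropriate will the fixed effects period and sequence be removed from the model".

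SAP 8.1.1 specifies an "analysis of variance model with fixed effects for product and a random effect for subject". SAP 9.2 declares this as a change from the protocol. It names no failed assumption and no check. Its only ground is that subjects may use their own nicotine products between the 8-hour sample and 10 pm, from which it concludes: "Hence, keeping period and sequence in the model adds no extra value to the analysis".

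The model's 90% interval decides the primary result: "If the CI falls within the range of 0.8-1.25, the corresponding two products are considered equivalent with respect to that comparison".

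**The concern.** Period is the term that removes day-to-day differences from a cross-over comparison. Evening use of own nicotine bears on pre-use nicotine level and carry-over. It does not show that Days 1 to 4 are exchangeable, and here it points the other way.

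- **Same for every period:** the overnight cut-off. Protocol 9.6.1 states "Subjects shall abstain from snus and all other nicotine containing products from 10 pm the evening prior" for each study day.
- **Different for Day 1:** the day before. Under Visit 2 the protocol says "Subjects are allowed to use their own snus or nicotine pouch product until 10 pm of Day -1", with no stated start limit. Before Days 2, 3 and 4, own use is allowed only from the 8-hour sample to 10 pm. If IP use starts between 7 and 10 am (assumed), that window is about 4 to 7 hours.

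A Day-1 versus Days 2-4 difference is therefore plausible, although the documents do not demonstrate one. If it exists and period is left out, it goes into the residual and widens every interval. If products are not evenly spread over days in the analysed set, it also biases the ratios to product D.

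Sequence matters much less. It is constant within a subject, so with complete data it cancels from the product contrasts.

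**Working it through.** The documents give no CV, period effect or power, so there is no planned figure to reproduce.

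**Inputs from the documents.** 27 randomised subjects; four cyclic sequences (A:B:C:D, B:C:D:A, C:D:A:B, D:A:B:C); 90% CI against 0.80-1.25.

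**Assumptions.** Day-1 log shift s of 0.1 to 0.3, either sign; within-subject CV 15-35%, with σ² = ln(1 + CV²).

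**1. Cost of keeping period.** Observations: 27 × 4 = 108. Residual df without period: 108 − 27 − 3 = 78; with period: 78 − 3 = 75. The t quantile moves from 1.6646 to 1.6654. At 7/7/7/6 with no period effect, the CI half-width for A/D at CV 30% is 0.1332 with period and 0.1330 without, a cost of about 0.1%. At 10/7/6/4 the cost is about 2%.

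**2. Loss of precision without period (7/7/7/6).** Within a subject the period effects (s, 0, 0, 0) have a sum of squares about their mean of s²(9/16 + 3/16) = 0.75s². Over 27 subjects this is 20.25s², which falls almost entirely into the residual:

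width ratio ≈ √[1 + 20.25s² / (78σ²)]

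At CV 25%, σ² = ln(1.0625) = 0.0606. With s = 0.2: √[1 + 0.81 / (78 × 0.0606)] = √1.171 = 1.08. Simulated widening agrees with this formula to within about one percentage point:

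| Shift | CV 15% | 20% | 25% | 30% | 35% |
|---|---|---|---|---|---|
| 0.1 | 5% | 3% | 2% | 1% | 1% |
| 0.2 | 21% | 12% | 8% | 6% | 4% |
| 0.3 | 43% | 26% | 18% | 13% | 10% |

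Simulated probability of concluding equivalence at true ratio 0.95 and CV 25% (product A against D, with the D-first sequence having 6 subjects) is 0.81 with period. Without it:

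| Size of shift | Positive | Negative |
|---|---|---|
| 0.1 | 0.81 | 0.78 |
| 0.2 | 0.79 | 0.73 |
| 0.3 | 0.76 | 0.66 |

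A different shape of period effect leads to the same conclusion. With a 10% drift per day at CV 30%, the CI is 8.6% wider and power at true ratio 1.00 is 0.67 without period against 0.74 with it.

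**3. Bias without period.** Let nX be the number of subjects who use product X on Day 1. With complete data:

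bias in log(X/D) = s(nX − nD)/27

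- 7/7/7/6: s × 1/27, giving 0.4%, 0.7% and 1.1% for s = 0.1, 0.2 and 0.3. Coverage of the 90% CI is 90-98%. False equivalence at a true ratio of 0.80 or 1.25 (CV 20-25%) is 0.01-0.06, against 0.05 with period.
- 9/8/5/5, s = 0.2: 0.2 × 4/27 = 0.030, a bias of about 3.0%. False equivalence at the nearer limit is 0.09-0.10.
- 4/6/7/10, s = 0.2: 0.2 × 6/27 = 0.0444, a bias of 4.3-4.5%. False equivalence at the nearer limit is 0.13-0.15 (CV 25-20%).

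In both unbalanced sets the rate with period is 0.05. When the bias runs in the opposite direction, the rate without period falls to about 0.01 or below.

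**4. How likely is imbalance?** Since 27/4 = 6.75, exact balance is impossible. SAP 4.5 says "A computer-generated randomisation list will be created by CTC using SAS Proc Plan, SAS Version 9.4 (or later") and gives no block size. Protocol 9.8.3 adds "Subjects who are prematurely withdrawn from the study for any reason may be replaced during the course of the study", and the PK analysis set excludes some subjects. If the list were unblocked (an assumption), exact multinomial sums give 0.026 for 7/7/7/6 in any order and 0.66 for some test product differing from D by 4 or more Day-1 users. With blocks of 4, imbalance beyond the unavoidable 7/7/7/6 split would come only from exclusions and replacements.

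**The case against.** The strongest reply has four parts.

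- **The change is open.** SAP section 9 declares it, and the protocol says 'if', not 'only if'. Both are true. The point is that the stated reason is weak, not that anything was hidden; and the natural reading of the protocol still requires an assumption to fail first.
- **The effect is assumed.** No passage supports a log shift of 0.1-0.3. At 0.1 the CI is only 1-5% wider and power barely moves. IP use is standardised and supervised, and baseline adjustment deals with residual nicotine. This limits the likely size. However, the adjustment addresses residual nicotine only, and SAP 8.1.1 clearly commits the adjusted values only to descriptive summary.
- **Near balance the error is conservative.** This stands: at 7/7/7/6 the loss is precision, and false equivalence is not materially raised.
- **The bias cases stack assumptions.** This stands too. The two unbalanced sets keep 27 analysed subjects, so exclusions from 7/7/7/6 cannot produce them. They need an unblocked list or several replacements placed in other sequences, plus a sizeable shift and a true ratio at the limit. Silence on block size does not show an unblocked list. Even if it were unblocked, the chance of a Day-1 difference of 6 or more, as in the 4/6/7/10 example, is 0.31.

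None of this supplies a reason to drop period. It limits the expected harm.

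**Conclusion.** The concern holds and should be fixed. The protocol makes removal conditional, the SAP makes it unconditional, and evening use of own nicotine does not justify it.

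The most likely consequence is modest: wider intervals and fewer equivalence conclusions if the days differ. Material bias and raised false equivalence arise only if the analysed sequences are also clearly unbalanced, which is hypothetical. All magnitudes rest on assumed shifts and CVs. The case for acting does not depend on them, because keeping period costs almost nothing and protects against both outcomes. No sample-size calculation was made, so there is no documented precision to spare.

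**What to change.** Withdraw SAP 9.2 and restore the protocol model in SAP 8.1.1: fixed product, period and sequence, random subject. Period is the essential term; sequence is harmless and keeps the SAP in line with the protocol. Report the product-only model as a sensitivity analysis at most. If the sponsor still wants a route to removing period, the SAP should name the assumption and the check that trigger it.

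A row giving PK analysis set counts by sequence in Table 14.1.2 would show the balance actually analysed; the shell gives that set only in total.

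The cost is one model statement and, if wanted, one table row before database lock, plus 3 of 78 residual degrees of freedom. The design, the randomisation list and data collection do not change.
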